#### 4. Study Procedures

##### a. Study design, including the sequence and timing of study procedures

This is an open-label randomized controlled trial. We will accrue 70 patients undergoing loading of oral DAPT (aspirin and ticagrelor 180mg [the latter only being administered if a stent procedure is necessary]) as part of routine clinical care. This may require that up to 300 patients will need to be approached for consent. The reason for this is that only about 1 in 4 patients who undergo left heart catheterization actually need DAPT loading for stent placement (many do not need stents) and it is impossible to know who these patients will be before the catheterization procedure is performed.

Consenting patients will be randomized, 1:1, to peri-procedural intravenous benzodiazepine plus non-systemic local analgesia or to the current standard of peri-procedural intravenous benzodiazepine plus intravenous fentanyl plus local analgesia (**figure**).

Peri-procedural analgesia is part of routine clinical care, thus, the primary research procedure in this study is the randomization to the type of analgesia (fentanyl vs. no fentanyl).

Subsequent to randomization, clinical care will then proceed as per normal practice (e.g. patients requiring coronary stenting will undergo the procedure at the discretion of the interventional cardiologist). However, because ticagrelor is a newer DAPT option and is less commonly given at our hospital than clopidogrel, we will require that patients enrolled into our study not be switched from ticagrelor to clopidogrel within the first 12 hours of the initial ticagrelor load in the catheterization lab (this is due to theoretical concerns that clopidogrel loading is less effective

within the first 12 hours of ticagrelor loading due to competition for platelet receptors). As such, we require all patients enrolled into the study to be admitted for observation for 12-24 hours after enrolment. Ticagrelor was chosen for this study as it is a potent and fast-acting agent, has been demonstrated to be superior to clopidogrel, and will allow us to answer the main research question as to whether, or not, fentanyl delays the GI absorption of oral anti-platelet agents.

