### b. Secondary outcome variables.

Additional secondary platelet outcomes will include light transmission aggregometry (LTA) at 2 hours, and also time-averaged PRU using mixed effects models. Given we hypothesize fentanyl may impair platelet inhibition due to reduced gastrointestinal absorption of ticagrelor, we will also compare ticagrelor pharmacokinetics in both arms, as determined by the area under the curve of active metabolite by liquid chromatography mass spectrometry (at 0, 0.5, 1, 2, 4 and 24 hours). We will also determine the impact of fentanyl on myocardial injury, as measured by high-sensitivity Troponin-I in the serum. In all 300 patients consented, we will also compare patient reported pain among both groups using the visual analog scale and the numeric rating scale (NRS). (12) These simple to perform subjective assessments can measure clinically meaningful differences in pain (e.g. a difference of 30% on the NRS). (12)

|   | YES                      | NO                       | Collection Date and TIME          |
|---|--------------------------|--------------------------|-----------------------------------|
| Pre Procedure Blood – Hour 0
• Platelet Function
- Verify Now  |  |  |    /    /    |
| Intra Procedure Blood- Hour 0.5
• Pharmacokinetics
• Platelet Function
- Verify Now   |  |  |    /    /    |
| Intra Procedure Blood- Hour 1
• Pharmacokinetics
• Platelet Function
- Verify Now   |  |  |    /    /    |
| Post Procedure Blood – Hour 2
• Pharmacokinetics
• Platelet Function
- Verify Now
- ADP-based LTA
• High Sensitivity Troponin
• Pain by Self-Report (visual scale) |  |  |    /    /    |
| Post Procedure Blood – Hour 4
• Pharmacokinetics
• Platelet Function
- Verify Now
• High Sensitivity Troponin  |  |  |    /    /    |
| Post Procedure Blood – Hour 24
• Pharmacokinetics
• Platelet Function
- Verify Now  |  |  |    /    /    |

*c. Statistical plan including sample size justification and interim data analysis.*

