Based on prior data , we anticipate a 2 hour PRU of ~230 (Standard Deviation of 25) among patients receiving 180 mg ticagrelor without opiate and estimate a conservative effect size of 20% increase in 2hr PRU among those who receive fentanyl . These calculations yield a sample size estimate of  $\leq 23$  subjects per group (approx. 50 total) to achieve 90% power (2 sided alpha 0.05). Accounting for drop out and unanticipated increases in 2hr PRU variability, and to provide power for subgroup analyses, we will accrue 70 patients who undergo DAPT loading in total. In all analyses a value of  $p < 0.05$  will be considered statistically significant.

*d. Early stopping rules.*

N/A

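### One p<0.05 rule covers the primary, six or seven secondary comparisons and unnamed subgroups, so the chance of at least one false 'significant' secondary result is roughly 20-30% if no secondary effect exists

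*Combined protocol and SAP*

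**What the plan says.** Section 7a names one primary outcome, mean PRU at 2 hours, and Section 7c sizes the trial on it ("2 sided alpha 0.05").

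Section 7b then lists the secondary outcomes. It begins: "Additional secondary platelet outcomes will include light transmission aggregometry (LTA) at 2 hours, and also time-averaged PRU using mixed effects models". It adds the AUC of ticagrelor's active metabolite, high-sensitivity troponin I, and pain on two scales (VAS and NRS). For troponin, the text gives neither a time point nor a summary measure; the sampling table in the same section draws it at hours 2 and 4.

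Section 7c closes with a general rule: "In all analyses a value of" p<0.05 "will be considered statistically significant". The same section gives power for subgroup analyses as one reason for raising accrual to 70, but names no subgroup factor.

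Section 2 words the secondary objectives as tests: one of a hypothesis about ticagrelor pharmacokinetics, the other of differences in pain and myocardial-injury markers. Nowhere does the document order the secondary outcomes, adjust for their number, or call them or the subgroups exploratory.

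**The concern.** The sentence in Section 7c does more than set a conventional alpha for the primary comparison. It gives every analysis the same right to be called statistically significant. If 2-hour PRU shows no difference, a single secondary or subgroup p-value below 0.05 may still be reported, within the plan as written, as a significant effect of fentanyl. The 5% error rate holds for each test alone. It does not hold for the set that the sentence covers, and a reader of the final report could not tell a planned confirmatory result from one of several chances.

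**Working it through.** **Is there a figure in the plan to reproduce?** The plan states no error rate for the set of tests. Its only calculated figure is the sample size, at most 23 per group. The stated inputs are a control mean of 230, SD 25, a 20% increase (46 PRU), 90% power and two-sided alpha 0.05. They give 2 × (1.960 + 1.282)² × (25/46)² = 6.2, so 7 per group (8 with the t distribution). An upper bound of 23 is not contradicted, but 23 does not follow from those inputs. That is a separate matter, and nothing below depends on it.

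**Step 1: count the secondary tests (Section 7b).**
1. LTA at 2 h
2. Time-averaged PRU
3. Metabolite AUC
4. Troponin I
5. Pain, VAS
6. Pain, NRS

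That makes six. The count is seven if troponin is tested separately at hours 2 and 4. The plan does not settle which.

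**Step 2: independent tests, all secondary nulls true.** The chance of at least one p<0.05 among k tests is 1 − 0.95^k.

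| k | 1 − 0.95^k |
|---|---|
| 5 (one troponin summary, one pain scale) | 22.6% |
| 6 | 26.5% |
| 7 | 30.2% |

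**Step 3: allow for correlation.** The documents give no correlations, so these are assumptions. LTA, PRU and AUC follow one drug pathway, VAS and NRS measure the same pain, and two troponin values come from the same patient. The check simulated 400,000 draws of multivariate normal test statistics, two-sided 0.05, with no correlation between the three groups of outcomes. Within groups, correlation was 0.3 to 0.7 for platelet and PK outcomes and 0.5 to 0.9 for troponin and for pain.

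| Tests | Lowest correlations | Highest correlations |
|---|---|---|
| 6 | 25.4% | 21.3% |
| 7 | 28.6% | 23.1% |

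A harsher assumption is one common correlation across all outcomes. At 0.5 it gives 20.6% (six) and 22.9% (seven). At 0.9, which is hard to credit between, say, pain and metabolite AUC, it gives 10.8% and 11.4%. None of these reaches 5%.

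**Step 4: subgroups.** Their number is not stated. As an illustration, one to three two-level factors add two to six within-subgroup tests of 2-hour PRU. Added to the seven secondary tests, under three of the Step 3 correlation settings (platelet and PK 0.3 to 0.5, the other two groups 0.5 to 0.8), with evenly split factors and overlapping patients allowed for, they give 31.8% (one factor, highest correlation) to 42.9% (three factors, lowest correlation).

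**Step 5: the primary.** It is one test at 0.05, and its error does not depend on how many secondary tests follow.

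**The case against.** The strongest reply is that this is a small mechanistic trial with one named primary outcome, and that formal adjustment of secondary outcomes in such a trial is partly a matter of preference. The document does rank the outcomes at the top level: Sections 2 and 7 separate primary from secondary, and Section 7c powers the primary alone. That stands. It is why the primary result is safe and why an exploratory label is enough. It does not answer the sentence in Section 7c, which removes that distinction at the point where significance is declared.

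Several stronger readings are tempting, and the documents do not support them:

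- **That 30% is a floor.** It is the value for seven independent tests. The text lists six comparisons, and positive correlation lowers the figure, so for the secondary outcomes 30% is close to a ceiling.
- **That the rate approaches one half.** Treating six subgroup tests as independent additions to the seven gives 1 − 0.95^13 = 48.7%. But the plan names no subgroup factors, and factors that split the same patients on the same outcome are not independent.
- **That the primary conclusion is inflated.** It is not.
- **That the plan would rest a change of practice on any isolated secondary p-value.** The Abstract, Section 3 and Section 9 link that prospect chiefly to reduced absorption together with raised platelet reactivity, not to a lone troponin, pain or subgroup finding.

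**Conclusion.** The point holds as a defect in a stated rule. Section 7c allows a claim of significance for every analysis, and error over the secondary and subgroup set is uncontrolled. If all secondary nulls are true, the chance of at least one false significant secondary result is 26.5% (six tests) to 30.2% (seven) under independence. It is roughly 20-30% under plausible positive correlation, or about four to six times the nominal 5%. The correlations are assumed, and the count depends on an unspecified troponin measure. Subgroups raise the figure, but by how much cannot be said from the documents. If some secondary effects are real, fewer true nulls remain and the chance of a false positive among them is smaller. The effect is on how secondary and subgroup results may be described; the primary comparison is untouched.

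**What to change.** Replace the closing sentence of Section 7c with:

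> The 2-hour PRU comparison, tested at two-sided 0.05, is the only confirmatory test. Secondary and subgroup results are exploratory and are reported as estimates with 95% CIs without a claim of statistical significance.

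If the sponsor wants formal secondary claims, test them only after a significant primary result, either in a fixed order or with Holm adjustment, using one prespecified troponin summary and one pain scale. That leaves five secondary tests, so the first Holm step would be at 0.05/5 = 0.01. The condition on the primary matters: Holm adjustment of the secondary outcomes as a separate family would still permit a significant secondary claim after a null primary, with error across the two families of up to about 1 − 0.95² = 9.75% if independent.

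The cost is wording only, with no extra patients, samples or visits. Some secondary and subgroup results lose the label 'significant'. The statement in Section 7c that accrual provides power for subgroup analyses must be reworded to match, and the subgroups should be named there.

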## **8. Risks**

*a. Medical risks, listing all procedures, their major and minor risks and expected frequency.*

It is possible that the non-systemic analgesia arm could report increased peri-procedural pain, however IV opiates are permitted at any time, for any participant, based on *break-through pain reported* during the case. The other main medical risks are the bleeding and bruising from venipuncture. Where possible we will draw blood from IV access to minimize venipuncture. As our research protocol includes the administration of ticagrelor as the anti-platelet agent used for the stenting procedure, some providers may wish to transition their patients from ticagrelor to other anti-platelet agents (such as clopidogrel or prasugrel) after completion of participation in our study. This change may be motivated by clinical or patient preference reasons. However, if the provider elects to make such a change after the participant has completed the study, we will require them to not change to either clopidogrel (starting with a 600mg load) or prasugrel (starting with a 60mg load) within the first 12 hours of the initial ticagrelor load (specifically, they will need to wait until 12 hrs has passed from the last ticagrelor dose and then load with the alternative agent at the time the next dose of ticagrelor would have been due. This requirement will minimize the risk that patients who are switched from ticagrelor to an alternative anti-platelet agent will not be exposed to the potential risk of suboptimal platelet inhibition in the period around which this change is made.

*b. Steps taken to minimize the risks.*

As already mentioned, blood will be drawn from existing iv heparin locks when available. Furthermore, we plan to minimize difference in pain by applying effective non-systemic analgesia that will consist of a rigorous pain relief strategy of potent benzodiazepine and effective local anaesthetic (e.g. subcutaneous lidocaine). In addition, patients can request more pain relief (including opiates) after the initial randomized analgesia has been allocated and can withdraw at any time from the study.

*c. Plan for reporting unanticipated problems or study deviations.*

Any unanticipated problems will be reported to the IRB.

*d. Legal risks such as the risks that would be associated with breach of confidentiality.*

Date will be stored on a secure and encrypted P.I.'s computer.

*e. Financial risks to the participants.*

There are no financial risks to the participants

**9. Benefits**

*a. Description of the probable benefits for the participant and for society.*

There are no guaranteed individual benefits for the participant. However, given the critical need for rapid inhibition of platelet function during PCI, this research proposal has true potential to change clinical practice, particularly if our results confirm reduced DAPT absorption and elevated residual platelet reactivity among patients receiving IV fentanyl during PCI. As such, this research could result in a paradigm shift in the analgesia management of PCI and have a profound impact on optimization of post-PCI clinical outcomes.

**10. Payment and Remuneration**

*a. Detail compensation for participants including possible total compensation, proposed bonus, and any proposed reductions or penalties for not completing the protocol.*

Subjects will not be compensated for participation in this study.

**11. Costs**

*a. Detail costs of study procedure(s) or drug (s) or substance(s) to participants and identify who will pay for them.*

The research performed on the blood samples will be paid for by the P.I. and not billed to the patient.

